4.2 ANTICIPATED ADVERSE DEVICE EFFECTS

In some very rare cases, some transitory troubles can appear such as conjunctiva mild irritation, foreign body sensation, ocular redness or burning or temporary blurred vision.

Horus Pharma	CIP #15E1122	Final Version 4.0 Date: 04/09/2017	Confidential Page 17/53
--------------	--------------	---------------------------------------	----------------------------

4.3 RESIDUAL RISKS ASSOCIATED WITH THE INVESTIGATIONAL DEVICE AS IDENTIFIED IN THE RISK ANALYSIS REPORT

DM05 is contraindicated in case of hypersensitivity to any component.

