4.6 STEPS THAT WILL BE TAKEN TO CONTROL OR MITIGATE THE RISKS

In case of adverse reaction to the studied MD, the subjects will be asked to call the investigator who will decide if the subject must stop the product use or not. The Investigator can prescribe a rescue treatment if needed.

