6.2.1.3 Precautions for use

DM05:

- For external use only.
- Do not swallow.
- Store at room temperature (below 25°C).
- Wash hands carefully prior to instillation.
- Always shake the vial before application.
- Do not touch the tip of the vial with hands, eyes or eyelids (risk of microbial contamination).
- Replace the protective cap on the tip of the vial after every use (risk of microbial contamination).

Horus Pharma	CIP #15E1122	Final Version 4.0 Date: 04/09/2017	Confidential Page 25/53
--------------	--------------	---------------------------------------	----------------------------

- Do not use if the vial is damaged (risk of microbial contamination).
- Maintain a minimum interval of 15 minutes between administration of two ophthalmic products.
- Do not use after the expiry date stated on the vial and the package (risk of microbial contamination).
- Keep out of reach and sight of young children.

Optive®

- Do not use if you are allergic to one of the constituent.
- Do not swallow.
- To avoid any contamination, ensure that the dropper does not touch any surface and avoid any direct contact with the eye.
- Carefully close the bottle after use.
- Do not use after the expiry date stated on the bottle
- Keep out of reach of children.
- Keep at room temperature.
- Do not use the bottle if the inviolability cap on the bottle neck is damaged before the first use of the product.
- Respect at least 5 minutes between administration of two ophthalmic products.

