6.3.2 Exclusion criteria for subject selection

- Pregnant or nursing woman or planning a pregnancy during the study.
- Subject who had been deprived of their freedom by administrative or legal decision.
- Subject in a social or sanitary establishment.
- Major subject who is under guardianship or who is not able to express his consent.
- Subject being in an exclusion period for a previous study.
- Subject suspected to be non-compliant according to the Investigator's judgment.
- Subject wearing contact lenses during the study.
- Far best corrected visual acuity $< 1/10$.
- Subject with severe ocular dryness with one of these conditions:
 - Eyelid or blinking malfunction
 - Corneal disorders not related to dry eye syndrome
 - Ocular metaplasia
 - Filamentous keratitis
 - Corneal neovascularization
- Subject with severe meibomian gland dysfunction (MGD).
- Within the last 3 months prior to the inclusion, history of ocular trauma, infection or inflammation not related to dry eye syndrome.
- Within the last 12 months, history of ocular allergy or ocular herpes.
- History of inflammatory corneal ulcer, recurrent corneal erosion, uveitis.
- Refractive or cataract surgery within the last 6 months.
- Any laser other than refractive surgery within the last 3 months.
- Any troubles of the ocular surface not related to dry eye syndrome.
- Ocular hypertension or glaucoma needing an hypotonic treatment
- Subject having used artificial tears in the 6 hours preceding the inclusion visit.
- Use during the month preceding the inclusion or during the study of: isotretinoid, cyclosporine, tacrolimus, sirolimus, pimecrolimus. punctual plugs.
- Any not stabilized systemic treatment, which can have an effect on performance or safety criteria, at the investigator appreciation.

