6.4 PROCEDURES

6.4.1 Description of all the clinical-investigation-related procedures that patients undergo during the clinical investigation

Selection visit (D-14 to D -7)

- The ophthalmologist will propose to his/her patient to participate to the clinical investigation.
- Information of the patient on study aims and schedule.
- Signature of information sheet and consent form in two copies by the patient and the investigator.
- Collection of previous medical and ophthalmological history, previous and actual treatments, demographic data.
- The ophthalmologist will evaluate the Ocular Surface Disease Index, the global ocular staining (Oxford score) and will realize the Schirmer test and TBUT.
- Checking of inclusion and exclusion criteria.
- If the patient is eligible, distribution of Hydrabak® to be used three times per day in both eyes until the inclusion visit, as well as a daily log to write eventual concomitant treatments and adverse events.

Inclusion visit (D0)

- The patient will bring back the Hydrabak® and the daily-log completed.
- Collection of adverse events and concomitant treatments.
- The ophthalmologist will evaluate the Ocular Surface Disease Index, the global ocular staining (Oxford score) and will realize Schirmer test and TBUT.
- Checking of inclusion and exclusion criteria.
- If the patient is eligible, inclusion of the patient and attribution of a randomization number.
- The ophthalmologist will evaluate the Van Bijsterveld score.
- The patient will evaluate his/her ocular symptoms.
- A third person will distribute the treatment according to the randomization list and explain the mode of use of the treatment, as well as a daily log to write eventual concomitant treatments and adverse events

D35

- The patient will bring back the treatments (used and non-used) and the daily-log completed.

- Collection of adverse events and concomitant treatments.
- The ophthalmologist will evaluate the Ocular Surface Disease Index, the global ocular staining (Oxford score), the Van Bijsterveld score and will realize Schirmer test and TBUT.
- The patient will evaluate his/her ocular symptoms.
- The patient and the investigator will evaluate the treatment performance on a 4-point scale.
- A third person will distribute the treatment according to the randomization list and remain the patient about the mode of use, as well as a daily log to write eventual concomitant treatments and adverse events.

D84

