14.7 INFORMATION REGARDING THE DATA MONITORING COMMITTEE (DMC), IF ESTABLISHED

Not applicable.

15- VULNERABLE POPULATION

Not applicable. The population studied during the clinical investigation is not considered as a vulnerable population

16- SUSPENSION OR PREMATURE TERMINATION OF THE CLINICAL INVESTIGATION

16.1 CRITERIA AND MODALITIES OF PREMATURE END OF TREATMENT OR SUBJECT EXCLUSION FROM THE CLINICAL INVESTIGATION

Subjects will be free to withdraw from the study at any time if they wish so and for any reason, without having to provide any justification to the Investigator.

The Investigator has the right to withdraw a subject for any reason, for subject's best interests, including illness or adverse events.

The Sponsor may decide to withdraw subjects for major deviation to the CIP, for administrative reasons or for any other valuable reason ethically justified.

Subjects may discontinue the study for the following reasons:

1. *Subject consent withdrawal*: subjects have the right to exit from the study at any time and for any motive, without their right to treatment being affected.
2. *Medical reasons or adverse events*: the Investigator has the right to withdraw a subject in case of intercurrent illness or adverse events or if in the Investigator's opinion, continuation in the study would be detrimental to the subject's well-being.
3. *Appearance of an exclusion criterion*.

4. *Failure to follow-up:* if a subject does not come to the scheduled visits, several attempts have to be done to try to contact him/her; to obtain the reasons for non-attendance.
5. *Violations and deviations from the CIP.*
6. *Administrative reasons.*

16.2 CRITERIA FOR ACCESS AND TO BREAKING THE BLINDING/MASKING CODE DURING THE CLINICAL INVESTIGATION

The Investigator will receive a sealed code envelope for each patient entered in the study, for use in emergency. Each envelope will contain the identity of patient's treatment. A set of code envelopes will also be retained by the CRO and the Sponsor.

The code envelopes may only be opened in the case of an emergency, such as a Serious Adverse Event, that requires knowledge of the identity of the investigational product in order to manage the patient's condition.

If opened, the time, date and reason for opening the code envelope must be written on the envelopes and signed by the Investigator; the Sponsor must be immediately notified in this instance.

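### Known allergy to a component of DM05 or Optive is a stated bar to use but is not an exclusion criterion, so such a patient can meet the written criteria and be randomised

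*Protocol*

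**What the plan says.** **Product sections.** Protocol 2.1 (contra-indications) and 4.3 (residual risks) both state: "DM05 is contraindicated in case of hypersensitivity to any component". It is the only entry under 4.3. For the comparator, the Optive precautions in 6.2.1.3 read: "Do not use if you are allergic to one of the constituent". The DM05 precautions in the same section contain other prohibitions, such as "Do not use if the vial is damaged (risk of microbial contamination", but no line on allergy.

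**Eligibility.** The only exclusion that mentions allergy is "Within the last 12 months, history of ocular allergy or ocular herpes" (6.3.2, also in synopsis 1.5 and SAP 3.2.2). Two other exclusions come near it: ocular inflammation unrelated to dry eye in the previous three months, and ocular surface disorders unrelated to dry eye. No inclusion criterion requires the absence of component allergy.

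**Allocation.** Under 6.4.1 the criteria are checked at selection and again at D0. At D0 the next step is: "If the patient is eligible, inclusion of the patient and attribution of a randomization number". A third person then dispenses the product and explains its use.

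**After allocation.** Section 4.6 begins: "In case of adverse reaction to the studied MD, the subjects will be asked to call the investigator". Section 16.1 adds: "The Investigator has the right to withdraw a subject for any reason", and lists among the grounds for discontinuation: "Appearance of an exclusion criterion".

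**Data.** SAP 7.3 includes a yes/no item on allergic history within the medical history taken at selection.

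**The concern.** A contraindication known before the trial starts would normally be carried into the exclusion criteria, because the person checking eligibility works from that list. Here that step is missing for both products. In a randomised comparison the screening has to cover both arms before allocation, since nobody knows at that moment which product the patient will receive.

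What is at stake is participant safety and the internal consistency of the protocol. As written, a patient can satisfy every criterion and still be someone to whom the protocol says the allocated product should not be given. There are 13 centres in three countries (7 in France, 2 in Poland, 4 in Spain), and without a written criterion each centre decides for itself whether to ask and what to do with the answer.

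**Working it through.** No figure in the plan bears directly on this point, so the check is a comparison of texts.

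1. **Is there a stated bar to use?** Yes, for both products: DM05 in 2.1 and 4.3, Optive in 6.2.1.3.

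2. **Is it in any eligibility list?** No. The synopsis, 6.3.2 and SAP 3.2.2 are not identical in every item (6.3.2 has an extra line on past corneal ulcer, recurrent erosion and uveitis), but none names hypersensitivity or allergy to a product component. The inclusion lists (synopsis, 6.3.1, SAP 3.2.1) do not cover it either.

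3. **Do the nearest criteria catch it indirectly?** Only in part:
   - Component allergy that showed as ocular allergy within 12 months: excluded.
   - Component allergy with ocular inflammation unrelated to dry eye within 3 months, or with a current unrelated ocular surface disorder: excluded.
   - Ocular reaction to a component more than 12 months ago, now resolved: not excluded.
   - Known non-ocular allergy to a component, for example soy lecithin, which is in the DM05 formula in 2.7: not excluded.

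4. **What happens to the last two patients at D0?** If they meet the remaining criteria they are eligible under 6.4.1 and receive a randomisation number.

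5. **Which safeguards remain, and when do they act?**
   - Contraindication in 4.3: part of the plan from the outset, DM05 only, not listed as a criterion to be checked.
   - Investigator judgement, including withdrawal under 16.1: available before or after the first dose, but discretionary.
   - Optive precaution in 6.2.1.3: before use, Optive only, and an instruction for use rather than an eligibility check.
   - Section 4.6: only after a reaction.
   - The 16.1 ground on exclusion criteria: does not reach component allergy while that is not an exclusion criterion.

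   None of these is an eligibility check before allocation.

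6. **Does it touch the statistics?** The sample size rests on a margin of 2 points, an SD of 2.5, 90% power, a two-sided 95% interval and 15% drop-out. With 34 per group and a true difference of zero, the noncentral-t power is 0.9015, and 68 / 0.85 = 80 randomised, so the plan's figures reproduce. None of these inputs depends on the missing criterion. A patient randomised and then stopped before any dose would be in the ITT population but in neither the safety population nor its per-protocol subset, and would not be replaced (6.1.7). The plan allows 80 − 68 = 12 such losses from all causes.

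**The case against.** The strongest reply is that the contraindication is already in the protocol. Section 10.1 forbids investigators to deviate from the plan, section 11 puts dispensing under a study-approved physician, and allergic history is taken at selection, 7 to 14 days before allocation. The physician therefore has both the warning and the information in time. For a patient to be exposed, a known allergy would have to go unasked or be disregarded. The CRF, investigator's brochure and product leaflets are not among the documents, and any of them may prompt the question. The effects described for DM05 are very rare and transitory.

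Much of this stands, and it limits the point to a minor one. It does not remove it: a warning in a risk section is not an item on the eligibility checklist, and nothing supplied links the allergy history to eligibility.

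Three stronger readings are tempting, and the documents do not support them:

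- A reader might infer that nothing can stop the first instillation. Section 16.1 is not tied to a reaction or to exposure. If the allergy is recognised between randomisation and dispensing, the investigator can withdraw the patient before any dose.
- A reader might infer that both arms are equally unprotected. Optive has a written instruction before use and the DM05 precautions have none, so the gap is weaker for Optive.
- A reader might take the SAP listings as evidence that allergy is not screened, because the ophthalmological-history and medication listings (SAP 7.3 and 7.4) carry a field for items preventing inclusion and the allergy listing names none. Those listings are produced after database lock and screen nobody, SAP section 9 describes planned listings as subject to change, and they do not show what the CRF contains.

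**Conclusion.** The omission is real and can be verified by reading: a bar to use stated for both products is absent from all three exclusion lists, and the nearest criteria leave non-ocular and older component allergy uncovered. The severity is minor.

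The documents give no frequency of component allergy, so neither a probability nor an expected number of patients can be stated. A reader might infer that serious harm is likely; the documents do not say so. They describe only very rare, transitory effects and do not discuss patients who are already sensitised. Nor is there a threat to the non-inferiority conclusion.

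The conclusion assumes that eligibility is judged on the listed criteria, as 6.4.1 indicates. If an unseen site form already asks about component allergy, the practical risk is smaller, but the protocol and SAP lists would still be inconsistent with the contraindication.

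**What to change.** Add one exclusion to synopsis 1.5, section 6.3.2 and SAP 3.2.2: known hypersensitivity or allergy to any component of DM05 or Optive. Check it at selection and at D0 against the allergy history already collected. For DM05 the components are given in 2.1 and 2.7. For Optive the sites need the product leaflet, because the protocol and SAP do not list its constituents. Once the item is listed, an allergy that comes to light after randomisation also falls under the 16.1 ground on exclusion criteria.

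No change to the SAP listings is needed. The cost is one amendment under section 9 and a possible, probably small, loss of recruits, which the documents do not allow to be sized. No new procedure is required, and no sample-size input changes.

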4.4 RISKS ASSOCIATED WITH PARTICIPATION IN THE CLINICAL INVESTIGATION

There will not be additional risks for the patients, associated with their participation in the clinical investigation.

4.5 POTENTIAL INTERACTIONS WITH CONCOMITANT MEDICAL TREATMENTS

Maintain a minimum interval of 15 minutes between instillation of another eye drops.

4.6 STEPS THAT WILL BE TAKEN TO CONTROL OR MITIGATE THE RISKS

In case of adverse reaction to the studied MD, the subjects will be asked to call the investigator who will decide if the subject must stop the product use or not. The Investigator can prescribe a rescue treatment if needed.

4.7 RISK-TO-BENEFIT RATIONALE

The benefits for the patients will be a possible improvement of their ocular symptoms and signs associated to ocular dryness.

On the other hand, no specific risk has been identified with the use of this medical device, except the following events that can also be observed with similar devices: stinging or eye glued sensation related to the instillation of the product in the eye.

The balance benefit-risk is then more in favor of the benefits.

5- OBJECTIVES AND HYPOTHESES OF THE CLINICAL INVESTIGATION

5.1 MAIN OBJECTIVE

To demonstrate the non-inferiority of DM05 in comparison with OptiveTM, in terms of cornea and conjunctiva staining (Oxford score) on patients with moderate to severe ocular dryness, after 35 days of treatment.

5.2 SECONDARY OBJECTIVE(S)

- To evaluate the efficacy of DM05 in comparison with OptiveTM on other signs and symptoms associated to moderate to severe ocular dryness, after 35 and 84 days of treatment.
- To evaluate the safety of DM05 over 84 days of treatment.

5.3 PRIMARY AND SECONDARY HYPOTHESES TO BE ACCEPTED OR REJECTED BY STATISTICAL DATA FROM THE CLINICAL INVESTIGATION

Non-inferiority of DM05 in comparison with OptiveTM, in terms of cornea and conjunctiva staining (Oxford score) after 35 days of treatment on worse eye, with a limit of non-inferiority equal to 2.

5.4 RISKS AND ANTICIPATED ADVERSE DEVICE EFFECTS THAT ARE TO BE ASSESSED

Non applicable.

	PRM02-F-012_A_V1 Clinical investigational plan for MD
---	--

6- DESIGN OF THE CLINICAL INVESTIGATION

6.1 GENERAL INFORMATION

6.1.1 Description of the type of clinical investigation

The clinical investigation will be:

- ◆ single blind (investigator-blinded)
- ◆ randomized
- ◆ in parallel groups,
- ◆ versus comparator,
- ◆ multicentric in France, Poland and Spain,
- ◆ on ambulatory patients.

6.1.2 Description of the measures to be taken to minimize or avoid bias

Because the comparator will be in commercial packaging, the blinding of the subject is not possible.

However, the study will be blinded for the investigator: evaluations will be done by an independent investigator, different than the person who will distribute the product. Subjects will be identified by a patient number. Each patient number will be associated to a treatment number, according to a randomization list provided before the beginning of the clinical investigation, and randomized either in one of both treatment groups (DM05 or Optive®).

6.1.3 Primary and secondary endpoints with rationale for their selection and measurement

6.1.3.1 Primary endpoint

Evaluation of the non-inferiority of DM05 in comparison with Optive™, in terms of cornea and conjunctiva staining (Oxford score), on worse eye, between D0 and D35.

6.1.3.2 Secondary endpoints

- Comparison of D35 versus D0 and D84 versus D0 for each product and comparison between products for the following parameters:
 - Evolution of cornea and conjunctiva staining (Oxford score on a scale) on worse eye.
 - Evolution of OSDI score (Ocular Surface Disease Index).
 - Evolution of Van Bijsterveld score (Lissamine green staining) in worse eye.
 - Evolution of Schirmer test result in worse eye.
 - Evolution of Tear film Break-Up Time (TBUT) in worse eye.
 - Evolution of ocular dryness severity by evaluation of each main symptom by the patient and total score of all symptoms
 - Evaluation of treatment performance by the investigator and the patient.
 - Collection of adverse events and adverse device effects.
- Evaluation of the average frequency of use during 84 days for DM05 and Optive™.

6.1.4 Methods and timing for assessing, recording and analysing variables

At selection and inclusion visits (D-14 to D-7 and D0), evaluations will be done on both eyes.

On D0, the worse eye will be defined as follows:

- If only one eye is eligible (i.e., fulfills all ophthalmological inclusion criteria with no ophthalmological exclusion criteria), the study eye is the eligible eye.

[figure not shown]
[figure not shown]
- If both eyes are eligible, the worse eye will be the eye with the highest Oxford score. If both eyes have the same Oxford score, the worse eye will be the eye with the highest Van Bijsterveld Score. If both eyes have the same Van Bijsterveld Score, the worse eye will be the eye with lowest Schirmer test result or lowest TBUT, if both eyes have the same scores, the worse eye will be the right eye.

On D35 and D84, all evaluations except symptoms evaluations (evaluation on average on both eyes) will be done only on the worse eye.

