6.1.4.1.4 Schirmer test

The Schirmer test is a method used to evaluate aqueous tear production.

It consists in inserting a strip (measuring 35 by 5 mm), without anaesthesia, over the lower lid margin of the eye during 5 minutes and then measuring the length of paper wetting in millimeters. The results is expressed in mm/5min.

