6.1.4.1.6 Ocular dryness symptoms

The subjects will score their ocular symptoms (**one global score for both eyes**) on structured scales from 0 to 10. These scales are presented below.

1. Discomfort

0	1	2	3	4	5	6	7	8	9	10
										
None						Very important				

2. Burning / stinging

0	1	2	3	4	5	6	7	8	9	10
										
None						Very important				

3. Eye dryness sensation

0	1	2	3	4	5	6	7	8	9	10
										
None						Very important				

4. Itching

0	1	2	3	4	5	6	7	8	9	10
										
None						Very important				

5. Sandy feeling / Foreign body sensation

0	1	2	3	4	5	6	7	8	9	10
										
None						Very important				

6. Photophobia

0	1	2	3	4	5	6	7	8	9	10
										
None						Very important				

7. Blurred vision

0	1	2	3	4	5	6	7	8	9	10
										
None						Very important				

In case of other symptom(s) declared by the patient, it will be also recorded in the CRF (free text).

The sum of all symptom scores will be calculated to obtain a score from 0 to 70.

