7.6.2 Secondary efficacy endpoint

- For the parameters hereafter: Oxford total score on worse eye, OSDI total score, Van Bijsterveld total score, Schirmer test result on worse eye, TBUT total score on worse eye, all ocular dryness symptoms score separately and then globally (total score):
 - For each product, description of the parameter at D0, D35 and D84.
 - For each product, description of the change of the parameter for each time-point (D35-D0 and D84-D0, relative and absolute variation).
 - A mixed ANOVA model (PROC MIXED) for repeated measures will be fitted to raw data, including the factor treatment as fixed (2 levels), time as fixed (3 levels: D0, D35 and D84), and product by time interaction, as well as the patient effect as random. From this model, the contrasts of interest will be built on the adjusted means:
 - To test whether each change from baseline (D35-D0 and D84-D0) differ significantly from 0 by product.
 - To test whether the products differ significantly for each change from baseline (D35-D0 and D84-D0).
 - The underlying assumptions (normality and homoscedasticity) will be checked using Shapiro-Wilk test and graphical representations of the residuals. In case of strong deviation, a non-parametric approach will be performed.
- For OSDI parameter, the different scores will be classified into the following categories:
 - OSDI None: OSDI (0 - <13)
 - OSDI Mild: OSDI (13 - <23)
 - OSDI Moderate: OSDI (23 - <33)
 - OSDI Severe: OSDI (33 - <100)

The parameter will be described at D0, D35 and D84 (with frequency and percentage)

A comparison of the different categories between products at D0, D35 and D84 will be performed, treatments groups will be compared with a Chi2 test.

- For the parameters hereafter: evaluation of performance by the patient, evaluation of performance for the investigator and frequency of use of the product:
 - The parameter will be described at D0, D35 and D84 (with frequency and percentage)
 - A comparison of the parameter between products at D35 and D84 will be performed: for the evaluation of performance by the patient and by the investigator, and for

frequency of use of the products, treatments groups will be compared with a Chi2 test.

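### Symptom scales are listed after the dyes and Schirmer strip, with both eyes tested at D0 but one at D35 and D84, which can favour apparent improvement in the within-product symptom tests

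*Protocol*

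**What the plan says.** **Eyes tested.** Protocol 6.1.4 sets the rule for the early visits: "At selection and inclusion visits (D-14 to D-7 and D0), evaluations will be done on both eyes". For follow-up it says: "On D35 and D84, all evaluations except symptoms evaluations (evaluation on average on both eyes) will be done only on the worse eye".

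**Unit of the symptom score.** Section 6.1.4.1.6 covers seven symptoms and a 0–70 total: "The subjects will score their ocular symptoms (one global score for both eyes) on structured scales from 0 to 10". It states no recall period. The OSDI (6.1.4.1.2), by contrast, asks about the last week.

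**Procedures.** Oxford staining and TBUT use fluorescein (6.1.4.1.1, 6.1.4.1.5). The Van Bijsterveld score uses lissamine green (6.1.4.1.3). The Schirmer strip is placed "without anaesthesia, over the lower lid margin of the eye during 5 minutes" (6.1.4.1.4).

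**Listed order.** Section 6.4.1 gives bullet lists for each visit:
- D0: OSDI, Oxford, Schirmer and TBUT; eligibility check; inclusion and randomisation number; Van Bijsterveld; then "The patient will evaluate his/her ocular symptoms"; then dispensing.
- D35 and D84: OSDI, Oxford, Van Bijsterveld, Schirmer and TBUT; then the symptom rating; then treatment performance.

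**Analysis.** Change in symptoms within each product is a declared secondary endpoint (Protocol 6.1.3.2). Among the planned contrasts, SAP 7.6.2 includes "To test whether each change from baseline (D35-D0 and D84-D0) differ significantly from 0 by product". It also plans a between-product comparison of the same changes. SAP 6.5 marks multiplicity as not applicable.

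**The concern.** Several of the rated items (discomfort, burning or stinging, foreign-body sensation, photophobia, blurred vision) are sensations that a dye or a paper strip could plausibly provoke. As listed, the baseline rating follows tests in two eyes and each follow-up rating follows tests in one, yet the patient gives one score covering both eyes throughout. Any irritation that lasts until the rating therefore weighs more at D0 than later, and falls after baseline whatever the product does.

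The tests exposed are the within-product changes. Seven symptoms plus the total, at two time points, for two products, make 8 × 2 × 2 = 32 tests against zero in each analysis population, without multiplicity adjustment. There is no untreated arm, so a fall in procedural irritation cannot be told apart from a product effect in these tests. They could nonetheless be read as showing that a product significantly improved symptoms.

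**Working it through.** **1. The plan's own figure.** The documents give no sample size, SD or expected change for symptoms. The only stated calculation is for the Oxford endpoint, and it supplies the numbers per arm. With margin 2, SD 2.5, one-sided 2.5% and 90% power, the normal formula gives n = 2 × (1.960 + 1.282)² × 2.5² / 2² = 32.8, so 33 per arm. The t-based version gives 34 per arm (power 0.902), or 68 in total, and 68 / 0.85 = 80 randomised. This reproduces, and the present point does not alter it.

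**2. Direction.** Assume that testing both eyes adds d points to an affected item, that testing one eye adds d/2 (the patient averages the eyes, as 6.1.4 describes), and that there is no true change. The spurious change per item then depends on when the rating is made:

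| Rating made | D0 | D35/D84 | Change |
|---|---|---|---|
| After tests at all visits (as listed) | d | d/2 | −d/2 |
| After tests at D0, before them later | d | 0 | −d |
| Before tests at D0, after them later | 0 | d/2 | +d/2 |
| Before tests at all visits, or usual symptoms rated | 0 | 0 | 0 |

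The listed order favours apparent improvement. An unfixed order could enlarge, reverse or remove the shift.

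**3. What a given d would do to a within-product test.** None of these inputs is in the documents: d of 0.5 to 2 points, an SD of change of 2 to 3 for one item, and 6 to 10 for a sum of three affected items. For k items the shift is k × d/2, with noncentrality (k × d/2) / (SD/√n). For example, k = 1, d = 1, SD 2 and n = 34 give 0.5 / (2/5.83) = 1.46 and a rejection rate of 29.3%. The test is a two-sided one-sample t at 5%, as an approximation to the mixed-model contrast in SAP 7.6.2.

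| d | Items | Shift | Rejection, n = 34 | Rejection, n = 40 |
|---|---|---|---|---|
| 0.5 | 1 | −0.25 | 7.6–10.9% | 8.1–12.0% |
| 1 | 1 | −0.5 | 15.7–29.3% | 17.7–33.8% |
| 2 | 1 | −1.0 | 47.1–80.8% | 53.8–86.9% |
| 0.5 | 3 | −0.75 | 7.1–10.9% | 7.5–12.0% |
| 1 | 3 | −1.5 | 13.6–29.3% | 15.2–33.8% |
| 2 | 3 | −3.0 | 39.7–80.8% | 45.7–86.9% |

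At d = 0 the rate is the nominal 5%. The table shows how sensitive the test would be. It does not estimate d.

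**4. Between products.** If both arms share the shift, the difference in change is −d/2 − (−d/2) = 0. A simulation with a common shift of −1.5, SD 6 and 34 per arm gave a mean difference of about 0 (−0.01) and a type I error of 4.9%.

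**The case against.** The strongest objection is that the sequence is inferred. Section 6.4.1 consists of bullet lists. Nothing there, in 6.1.4 or in the visit schedule makes the order binding or sets an interval between test and rating. The bullets can be read as grouped by who acts: ophthalmologist, patient, third person. At D35 TBUT stands after lissamine green and Schirmer, although it shares fluorescein with the Oxford grading, so the list is weak evidence of actual practice. Momentary rating is also an inference: the absence of a recall period is all the text shows, and patients may rate their usual dry-eye symptoms. Irritation must also last until the rating.

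Most of this stands, and it is why the point is conditional. It does not remove the point. At D0 the list does read as a sequence up to inclusion, because eligibility needs the Oxford score plus Schirmer or TBUT, and the symptom rating is listed beyond that step. Nothing tells a site to rate first. The two-eye versus one-eye difference is explicit and needs no inference.

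A second objection is that uncontrolled before–after tests could not isolate a product effect anyway. Patients are selected for active signs and symptoms after a saline wash-out. Artificial tears are withheld for six hours before D0, with no matching rule stated for the later visits. This is right, and it supports labelling these changes descriptive.

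A reader might infer more: that improvement is built into the symptom results, or that irritation blurs real differences between products. The documents support neither. The first needs a binding order, momentary rating and lasting irritation, none of which is stated. No calculation supports the second.

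**Conclusion.** The point holds in conditional form. Followed as listed, with patients rating current sensation, the procedure loads more test irritation onto D0 than onto D35 or D84. That favours apparent improvement in both arms' within-product symptom changes. The shift is half of the irritation that two-eye testing adds to each affected item, assuming patients average their eyes. That irritation is not given in the documents and could be zero. The rejection rates shown run from near nominal to over 80% solely because of the assumed inputs, so they should not be cited as the size of the problem.

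The reach is limited. The primary endpoint is graded by the investigator on the worse eye, so it and the sample size are unaffected. The between-product symptom comparison is not shifted on average, provided the irritation is common to both arms. The OSDI is less exposed: it is listed first and asks about the last week. This is a cheap improvement to a secondary endpoint and does not threaten the trial's main conclusion.

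**What to change.** - **Protocol 6.4.1, 6.1.4.1.6 and the visit schedule (6.1.5):** state that the symptom scales and the OSDI are completed on arrival at D0, D35 and D84, before any drop, dye or strip.
- **Patients already past D0:** those whose D0 rating was made in the old order keep that order to D84 and are flagged. Because the list was never binding, the flag should record the order actually used, where the site can establish it.
- **SAP 7.6.2:** report within-product symptom changes as descriptive, shown by assessment order, and base symptom conclusions on the between-product comparison.
- **Recall period:** leave it unchanged. Adding a last-week window mid-trial would change the instrument.

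No visit, procedure or patient is added. The cost is a minor amendment, handled under Protocol section 9 with centres in three countries, plus e-CRF guidance and a short SAP change. The remaining downside is two assessment orders in the data, for patients enrolled before and after the amendment. If every patient is already past D0, only the flag and the SAP change apply.
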